4.3 Justification for Dose

Regorafenib dose

Regorafenib PK has been well characterized in patients with various solid tumors including HCC patients. In the dose-finding study 11650, regorafenib PK was investigated for dose levels of 10 mg, 30 mg, 60 mg, 120 mg, 160 mg up to 220 mg QD with a schedule of 3 weeks on / 1 week off. The regorafenib dose of 160 mg QD for the first 3 weeks of each 4-week cycle was declared as the MTD/RP2D based on exposure and a positive benefit-risk profile. This dosing regimen was further evaluated in several pivotal Phase 3 studies and approved worldwide, as monotherapy, in several indications including 2L HCC.

Recently, clinical evidence has been generated suggesting an increased benefit with the combination of regorafenib and anti-PD-1 agents such as pembrolizumab or nivolumab. The REGONIVO study is an open-label, dose-finding, and dose-expansion Phase 1b trial of regorafenib and nivolumab in patients with advanced microsatellite-stable CRC and gastric cancer (Fukuoka et al. 2019). In this study, the combination was shown to be tolerable and an encouraging 40% objective response rate was observed as compared to the historical response rate of regorafenib monotherapy in this population of 1-2% (Grothey et al. 2013). The MTD for regorafenib in this combination, based on pre-defined dose-limiting toxicity (DLT) criteria, was deemed to be 120 mg. However, in the first 18 participants treated at the 120 mg dose of regorafenib in the dose expansion cohort, all but one required dose reduction to 80 mg for AEs mostly related to Grade 3 skin toxicities. All remaining participants (N=18) were treated with a regorafenib starting dose of 80 mg and tolerated treatment well. Regorafenib exposure is similar across tumor types (CRC vs. HCC) and has shown comparable tolerability, so the results from the Phase 1 study mentioned above were considered for dose selection of the planned Phase 3 study in HCC.

Page 40 of 141

The ongoing Phase 1b study, 19497, designed to investigate regorafenib in combination with pembrolizumab as 1L treatment in patients with HCC, has declared regorafenib 120 mg QD at a schedule of 3 weeks on / 1 week off as the MTD. Out of 18 evaluable participants for DLT, four had DLT events including Grade 3 HFSR, Grade 3 liver function test (LFT) increase accompanied with Grade 2 bilirubin increase (2 each). Based on the modified toxicity probability interval (mTPI) study design, regorafenib 120 mg daily 3 weeks on / 1 week off in combination with pembrolizumab was defined as the MTD for this combination however, the dose of 120 mg is associated with a relatively high incidence of dose reduction and discontinuation and a new expansion cohort has been opened for recruitment to evaluate 80 mg QD (3 weeks on / 1 week off) in NOV 2019. The combination indicated a preliminary efficacy signal. As of NOV 2020, preliminary efficacy data show PR by RECIST 1.1 in 9 out of the 31 participants who started 120 mg regorafenib QD (3 weeks on / 1 week off) and were evaluable for efficacy.

As a result of the high discontinuation rate associated with the 120 mg dose as well as the results from the REGONIVO study, the planned Phase 2 study will use a regorafenib starting dose level of 90 mg QD in cycle 1, if tolerated, escalating to 120 mg any time after the first cycle of regorafenib in a 3 weeks on / 1 week off schedule (for details on dose modification, see Section 6.6).

The rationale for changing from an 80 mg starting dose to a 90 mg starting dose is based on emerging data from ongoing clinical studies (Fukuoka et al. 2019) of regorafenib in combination with IO (e.g. nivolumab or pembrolizumab), where 80 mg is the currently recommended starting dose with the option to escalate to 120 mg in patients who can tolerate it. However, a number of patients who start at a dose of 80 mg still require dose reductions due to safety/tolerability. With the currently available 40 mg tablet, the only options are to reduce to 40 mg QD which is a 50% dose reduction or to 80 mg every other day (QOD) which is more difficult for patient compliance and still a 50% dose reduction. Therefore, the sponsor is proposing a new tablet strength of 30 mg for regorafenib in combination with IO. A 30 mg tablet would allow for a starting dose of 90 mg QD for the first 3 weeks of each 4-week cycle. Due to the high inter-subject PK variability, a dose of 90 mg is expected to provide very similar exposure to the currently recommended combination starting dose of 80 mg. A 30 mg tablet also will allow for a dose modification step to 60 mg which is a more conventional 33% dose reduction as compared to 50% with the 40 mg tablet.

Pembrolizumab dose

The planned dose of pembrolizumab for this study is 400 mg Q6W.

A 400 mg Q6W dosing regimen of pembrolizumab is approved by the US FDA for use in both monotherapy and combination therapy settings. This dosing regimen is expected to have a similar benefit-risk profile as 200 mg Q3W, in all indications in which 200 mg Q3W pembrolizumab is currently appropriate (Lala et al. 2018). Specifically, the dosing regimen of 400 mg Q6W for pembrolizumab is considered adequate based on modeling and simulation (M&S) analyses, given the following rationale:

- PK simulations demonstrating that in terms of pembrolizumab exposures
 - Average concentration over the dosing interval (C_{avg}) (or area under the curve [AUC]) at 400 mg Q6W is similar to that at the approved 200 mg Q3W dose, thus bridging efficacy between dosing regimens.

Page 41 of 141

- Trough concentrations (C_{min}) at 400 mg Q6W are generally within the range of those achieved with 2 mg/kg or 200 mg Q3W in the majority (>99%) of patients.
- Peak concentrations (C_{max}) at 400 mg Q6W are well below the C_{max} for the highest clinically tested dose of 10 mg/kg every 2 weeks (Q2W), supporting that the safety profile for 400 mg Q6W should be comparable to the established safety profile of pembrolizumab.
- Exposure-response (E-R) for pembrolizumab has been demonstrated to be flat across indications, and OS predictions in melanoma and non-small cell lung cancer (NSCLC) demonstrate that efficacy at 400 mg Q6W is expected to be similar to that observed at 200 mg Q3W.

4.4 End of Study Definition

The end of the study (EoS) as a whole will be reached when the last visit of the last patient (LPLV) has been achieved in all participating centers.

LPLV of a participant is reached if he/she has completed the last scheduled procedure shown in the SoA (see Section 1.3; this also includes telephone contacts during long-term follow-up) unless the participant died or withdrew consent or is lost to follow-up.

Furthermore, to reach EoS, either the following criteria or both need to be satisfied in this study:

- All participants have disease progression or are no longer on study intervention (regorafenib and/or pembrolizumab).
- The last included participant has been followed for at least 2 years since the first study treatment administration or is deceased.

Decisions on trial termination, protocol amendment, or cessation of patient recruitment can be made by the sponsor at any point in the study, guided by the monitoring boundaries at the interim analysis of the pilot phase, cumulative safety review, or strategic expectations for the study compounds after primary completion has been reached.

If the study is stopped by the sponsor but benefits are observed for ongoing participants, further treatment options may be discussed and agreed between the investigator, sponsor, and the participant (for further information refer to Section 6.5.5). Therefore, the LPLV date may also be reached based on the last participant switching to a roll-over study, post-trial access program or being switched to commercial drug supply with no cost to the participant.

Primary completion

The primary completion date according to FDA Amendment Act is defined as date that the final participant was examined or received an intervention for the purposes of final collection of data for the primary outcome. In this trial, the primary completion is defined as when all evaluable participants in the expansion phase have been assessed for objective response rate as defined by RECIST 1.1.

Participants are considered evaluable for efficacy once they have completed at least two post-baseline scans or have been followed for approximately 14 weeks from the first study treatment dose, unless they have discontinued before due to progression or any other reason.

Page 42 of 141

5. Study Population

Prospective approval of protocol deviations to recruitment and enrollment criteria, also known as protocol waivers or exemptions, is not permitted.

5.1 Inclusion Criteria

Inclusion criteria must be met at the time of screening unless otherwise specified.

Participants are eligible to be included in the study only if all of the following criteria apply:

Age

1. \geq 18 years of age on the day of signing informed consent.

Type of Participant and Disease Characteristics

- 2. Histological or cytological confirmation of HCC or non-invasive diagnosis of HCC as per American Association for the Study of Liver Diseases (AASLD) criteria (see Appendix 11, Section 10.11) in cirrhotic participants.
- 3. Unresectable advanced HCC eligible for systemic therapy.
- 4. Participants must have progressed after only one prior line of systemic immunotherapy treatment with an anti-PD-1/PD-L1 mAb administered either as monotherapy or in combination with other checkpoint inhibitors or other therapies (for prior therapy in the cohorts in the pilot phase see Section 4.1). A wash out period of at least 28 days or 5 half-lives, whichever is shorter, must be completed for eligibility in this trial. PD-1/PD-L1 treatment progression is defined by meeting all of the following criteria:
 - a. Has received at least 2 doses of an approved anti-PD-1/PD-L1 mAb or received PD-1/PD-L1 treatment for 8 weeks, whichever is longer.
 - b. Has demonstrated disease progression after PD-1/PD-L1 treatment as defined by RECIST 1.1 (see Appendix 5, Section 10.5.1). In the absence of rapid clinical progression, the initial evidence of RECIST 1.1 disease progression is to be confirmed using iRECIST (see Appendix 5, Section 10.5.3) by a second assessment no less than four weeks from the date of the first documented progressive disease.
 - i. This determination is made by the investigator. Once progressive disease is confirmed, the initial date of RECIST 1.1 progressive disease documentation will be considered that date of disease progression.
 - ii. In cases of unequivocal clinical or radiological progression, disease progression confirmation may not be required after documented discussion and approval by the sponsor.
 - c. Progressive disease has been documented within 12 weeks from the last dose of anti-PD-1/PD-L1 mAb.
- 5. Participants who receive anti-PD-1 therapy as adjuvant treatment following complete resection of liver cancer and have disease recurrence (unresectable locoregional disease or distant metastases) are eligible if they progressed while on active treatment or within 6 months of stopping anti-PD-1 therapy. This will be considered the first line of systemic therapy.

For these participants, the following applies:

- 1) a second assessment to confirm disease progression beyond recurrence is not required; and
- 2) they must have received at least 2 prior doses of anti-PD-1/PD-L1 mAb.
- 6. Barcelona Clinic Liver Cancer (BCLC) stage B or C (see Appendix 8, Section 10.8).
- 7. Liver function status should be Child-Pugh (CP) Class A (see Appendix 9, Section 10.9) within 7 days prior to the first dose of study intervention. CP status should be calculated based on clinical findings and laboratory results during the screening period.
- 8. Eastern Cooperative Oncology Group (ECOG) Performance Status (PS) of 0 or 1 within 7 days prior to prior to the first dose of study intervention.
- 9. At least one measurable lesion by CT scan or MRI according to RECIST 1.1. Tumor lesions situated in a previously irradiated area, or in an area subjected to other loco-regional therapy, may be considered measurable if there has been demonstrated progression in the lesion.
- 10. Have adequate organ function as defined in the following table (Table 5–1). Specimens must be collected within 7 days prior to the start of study intervention.

Table 5-1: Adequate Organ Function Laboratory Values

System	Laboratory Value
Hematological	
Absolute neutrophil count (ANC)	≥1000/mm³
Platelets	≥60 000/mm³
Hemoglobin	≥8.5 g/dL ^a
Renal	
Creatinine OR Measured or calculated ^b creatinine clearance (GFR can also be used in place of creatinine or CrCl)	≤1.5 × ULN OR ≥30 mL/min for participant with creatinine levels >1.5 × institutional ULN
Hepatic/Pancreatic	
Total bilirubin	≤2 mg/dL. Mildly elevated total bilirubin (<6 mg/dL) is allowed if Gilbert's syndrome is documented.
AST and ALT	≤5.0 × ULN
Lipase	≤ 3 x ULN without symptoms
Coagulation	
International normalized ratio (INR) OR prothrombin time (PT) Activated partial thromboplastin time (aPTT)	PT-INR <2.3 and aPTT <1.5 x ULN unless receiving treatment with therapeutic anticoagulation

Page 44 of 141

Table 5-1: Adequate Organ Function Laboratory Values

- ALT = alanine aminotransferase; aPTT = activated partial thromboplastin time; AST = aspartate aminotransferase; INR = international normalized ratio; CrCl = creatinine clearance; GFR = glomerular filtration rate; PT = prothrombin time; ULN = upper limit of normal.
- a. Criteria must be met without packed red blood cell (pRBC) transfusion within the prior 2 weeks. Participants can be on stable dose of erythropoietin (≥ approximately 3 months).
- b. Creatinine clearance (CrCl) should be calculated per institutional standard.
- Note: This table includes eligibility-defining laboratory value requirements for treatment; laboratory value requirements should be adapted according to local regulations and guidelines for the administration of specific chemotherapies.
 - 11. Participants with controlled (treated) hepatitis B virus (HBV) infection will be allowed if they meet the following criteria:
 - Antiviral therapy for HBV must be given for at least 4 weeks and HBV viral load must be less than 500 IU/mL prior to first dose of study intervention.
 - Participants on active HBV therapy with viral loads under 500 IU/ml should stay on the same therapy throughout study treatment.
 - Participants who are anti-HBc (+), negative for HBsAg, negative for anti-HBs, and have an HBV viral load under 500 IU/mL that do not require HBV antiviral prophylaxis.
 - 12. Participants may have a past or ongoing hepatitis C virus (HCV) infection. Participants must have completed their treatment at least 1 month prior to W1D1 or have received at least 1 month of direct acting antiviral (DAA) HCV therapy with no DAA related safety events and stable LFTs. For participants not on anti-HCV therapy at the time of study enrollment, DAAs for treatment of HCV infection can be initiated per the investigator's discretion, if LFTs are stable after 3-6 months of study intervention upon sponsor consultation.
 - 13. Provision of recent tumor tissue (as defined below) is mandatory at screening. Exceptions will be accepted for participants with no recent baseline tumor tissues after documented discussion and approval by the sponsor.
 - Tumor tissue obtained within 180 days of enrollment and after the last dose of most recent anti-cancer therapy.
 - Or a new biopsy.

Sex

- 14. Male and/or female who meet the requirements for contraception and breastfeeding as follows (additional contraception guidance is provided in Appendix 4, Section 10.4.2):
 - A male participant must agree to use highly effective contraception (see Appendix 4, Section 10.4.2) during the intervention period and for 120 days after the last dose of regorafenib and refrain from donating sperm during this period.
 - A female participant is eligible to participate if she is not pregnant (see Appendix 4, Section 10.4.3), not breastfeeding, and at least one of the following conditions applies:
 - a) Not a woman of childbearing potential (WOCBP) as defined in Appendix 4, Section 10.4.1.

Page 45 of 141

b) A WOCBP who agrees to follow the contraceptive guidance in Appendix 4, Section 10.4.2 during the study intervention period and for at least 120 days after the last dose of pembrolizumab, and 210 days after the last dose of regorafenib.

Informed Consent

15. Capable of giving signed informed consent as described in Appendix 1 (Section 10.1), which includes compliance with the requirements and restrictions listed in the ICF and in this protocol.

Participants must provide a signed informed consent before any screening procedures.

5.2 Exclusion Criteria

Participants are excluded from the study if any of the following criteria apply at the time of screening:

Medical Conditions

1. Pregnant or breastfeeding patients or expecting to conceive or father children within the projected duration of the study, starting with the screening visit through at least 120 days after the last dose of pembrolizumab, and 210 days after the last dose of regorafenib.

Note: A WOCBP who has a positive urine pregnancy test (e.g. within 72 hours) prior to treatment. If the urine test is positive or cannot be confirmed as negative, a serum pregnancy test will be required.

- 2. Fibrolamellar and mixed hepatocellular/cholangiocarcinoma subtypes.
- 3. Patients unable to swallow and retain oral medications.
- 4. Patients with disease that is suitable for local therapy administered with curative intent.
- 5. Patients who experienced any CTCAE ≥ 3 or any other immune-related toxicities that led to permanent discontinuation of treatment with immune checkpoint inhibitors in 1 L.
- 6. Persistent proteinuria of CTCAE Grade 3 or higher. Urine dipstick result of 3+ or abnormal, based on type of urine test strip used, is allowed if protein excretion (estimated by urine protein/creatinine ratio on a random urine sample) is <3.5 g / 24 hours.
- 7. Diagnosis of immunodeficiency or patient is receiving chronic systemic steroid therapy (in doses exceeding 10 mg daily of prednisone equivalent) or any other form of immunosuppressive therapy within 7 days prior to the first dose of study interventions. The use of physiologic doses of corticosteroids may be approved after consultation with the sponsor.
- 8. Active autoimmune disease that has required systemic treatment in past 2 years (i.e., with use of disease modifying agents, corticosteroids or immunosuppressive drugs). Replacement therapy (e.g., thyroxine, insulin, or physiologic corticosteroid

- replacement therapy for adrenal or pituitary insufficiency) is not considered a form of systemic treatment and is allowed.
- 9. History of (non-infectious) pneumonitis that required steroids or current pneumonitis.
- 10. History of interstitial lung disease.
- 11. Major surgical procedure or significant traumatic injury within 28 days before start of study medication.
 - Note: If the participant received major surgery, he/she must have recovered adequately from the toxicity and/or complications from the intervention prior to starting study treatment.
- 12. Non-healing wound, non-healing ulcer, or non-healing bone fracture.
- 13. Patients with evidence or history of any bleeding diathesis, irrespective of severity.
- 14. Any hemorrhage or bleeding event CTCAE Grade \geq 3 within 28 days prior to the start of study medication.
- 15. Patients with large esophageal varices at risk of bleeding that are not being treated with conventional medical intervention: beta-blockers or endoscopic treatment. Assessment of esophageal varices (see Appendix 10, Section 10.10) should be performed by endoscopy within 6 months of the start of study intervention. For patients in whom conventional medical intervention for known esophageal varices is already in place, assessment should be performed by endoscopy as per local standard of care.
- 16. Arterial or venous thrombotic or embolic events such as cerebrovascular accident (including transient ischemic attacks), deep vein thrombosis or pulmonary embolism within 6 months before the start of study medication (except for portal vein thrombosis and adequately treated catheter-related venous thrombosis occurring more than one month before the start of study medication).
- 17. History of organ allograft.
- 18. Known history of human immunodeficiency virus (HIV) infection (HIV 1/2 antibodies).
- 19. Ongoing infection CTCAE Grade > 2 requiring systemic therapy.
- 20. Dual active HBV infection (HBsAg (+) and / or detectable HBV DNA) and HCV infection (anti-HCV Ab (+) and detectable HCV RNA) at study entry.
- 21. Uncontrolled hypertension (systolic blood pressure ≥ 140 millimeter of mercury [mmHg] or diastolic pressure ≥ 90 mmHg) on more than 2 separate measurements despite optimal medical management.
- 22. Congestive heart failure of New York Heart Association (NYHA) class ≥2 (see Appendix 7, Section 10.7).
- 23. Unstable angina (angina symptoms at rest), new-onset angina (begun within the last 3 months).
- 24. Myocardial infarction less than 6 months before start of study intervention.
- 25. Uncontrolled cardiac arrhythmias despite optimal medical management.
- 26. Pleural effusion or ascites that causes respiratory compromise (CTCAE Grade ≥2 dyspnea). Note: Participants treated with thoracentesis/paracentesis within 14 days

- prior to signing informed consent are eligible if clinically stable and have recovered to dyspnea Grade ≤ 1 or baseline after the procedure.
- 27. Patients with previous malignancies (except non-melanoma skin cancers, and the following in situ cancers: bladder, gastric, colon, cervical/dysplasia, melanoma, or breast) are excluded unless a complete remission was achieved at least 3 years prior to study entry and no additional therapy is required or anticipated to be required during the study period.
- 28. Known active central nervous system (CNS) metastases and/or carcinomatous meningitis. Participants with previously treated brain metastases may participate provided they are radiologically stable, i.e., without evidence of progression for at least 4 weeks by repeat imaging (note that the repeat imaging should be performed during study screening), clinically stable and without requirement of steroid treatment for at least 14 days prior to first dose of study treatment.
- 29. Seizure disorder requiring medication.
- 30. Significant acute gastrointestinal disorders with diarrhea as a major symptom e.g., Crohn's disease, malabsorption, or CTCAE Grade ≥2 diarrhea of any etiology.
- 31. Current evidence or suspicion of gastrointestinal perforation or fistula.
- 32. Known hypersensitivity (Grade ≥3) to any of the study interventions, study intervention classes, or excipients in the formulation.

Prior/Concomitant Therapy

- 33. Prior monotherapy treatment with any tyrosine kinase inhibitor in 1L.
- 34. Prior treatment with regorafenib, in combination regimens with immune checkpoint inhibitors.
- 35. Patients who received prior radiotherapy within 2 weeks of start of study treatment. Participants must have recovered from all radiation-related toxicities, not require corticosteroids, and not have had radiation pneumonitis. A 1-week washout is permitted for palliative radiation (≤2 weeks of radiotherapy) to non-CNS disease.
- 36. Patients who have received a live vaccine or live attenuated replication competent vaccine within 30 days prior to the first dose of study intervention. Seasonal injectable influenza vaccines and vaccines administered in a pandemic context are allowed.
- 37. Prior transplantation of human cells, tissues and organs (e.g. liver transplant) or candidates for any type of transplantation.
- 38. Transfusion of blood products (including platelets or red blood cells) within 7 days prior to signing informed consent, or administration of colony stimulating factors (including G-CSF, GM-CSF or recombinant erythropoietin) within 4 weeks prior to signing informed consent.
- 39. Patients on concomitant use of CYP3A4 inducers, strong CYP3A4 inhibitors (see Appendix 6 in Section 10.6) and strong UGT1A9 inhibitors (e.g. mefenamic acid, diflunisal, and niflumic acid) within 2 weeks prior to start of study intervention.

Prior/Concurrent Clinical Study Experience

40. Previous assignment to treatment during this study. Participants permanently withdrawn from study intervention will not be allowed to re-enter screening.

Page 48 of 141

- 41. Previous (at least a minimum of 28 days, or 5 half-lives of an investigational drug before the start of study treatment, whichever is shorter) or concomitant participation in another clinical study with investigational medicinal product(s).
- 42. Participants must have recovered from all AEs due to previous therapies to Grade ≤1 or baseline. Participants with treatment-related alopecia and Grade ≤2 neuropathy may be eligible.

Other Exclusions

- 43. History or current evidence of any condition, therapy, or laboratory abnormality that might confound the results of the trial, interfere with the patient's participation for the full duration of the trial, or is not in the best interest of the patient to participate, in the opinion of the treating investigator.
- 44. Known psychiatric or substance abuse disorders that would interfere with cooperation with the requirements of the trial.

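### Exclusion 38 counts its 7-day transfusion window back from consent, so it can miss a platelet transfusion given before the qualifying count; it also cancels the erythropoietin allowance in Table 5-1

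*Protocol*

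**What the plan says.** **Transfusion window.** Exclusion 38 (Protocol Section 5.2) bars "Transfusion of blood products (including platelets or red blood cells) within 7 days prior to signing informed consent". The other three timed criteria under the same sub-heading count from the start of treatment:
- 35: "Patients who received prior radiotherapy within 2 weeks of start of study treatment"
- 36: a live "vaccine within 30 days prior to the first dose of study intervention"
- 39: interacting drugs "within 2 weeks prior to start of study intervention"

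**Platelet limit.** Table 5-1 (Section 5.1, criterion 10) requires at least 60 000/mm³, with no footnote. Footnote a is attached to the hemoglobin limit and reads "Criteria must be met without packed red blood cell (pRBC) transfusion within the prior 2 weeks".

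**Timing of the sample.** Screening opens at consent and lasts up to 28 days before W1D1 (Section 4.1.1.1). Criterion 10 wants the specimens within 7 days before treatment starts. Table 10-1, footnote a, has older tests repeated on W1D1. Section 5.4 allows one re-test of an out-of-range result within 14 days, with sponsor approval and without a new consent. The opening text of Section 8 lets a routine blood count taken before consent serve for screening if it falls inside the scheduled window.

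**Erythropoietin.** Footnote a adds "Participants can be on stable dose of erythropoietin", for about 3 months or longer. Exclusion 38 bars colony stimulating factors, "including G-CSF, GM-CSF or recombinant erythropoietin) within 4 weeks prior to signing informed consent". Section 5.2 opens with "Participants are excluded from the study if any of the following criteria apply at the time of screening", and Section 5 permits no waivers.

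**The concern.** The platelet limit is a safety limit for entry to treatment with a drug for which the protocol takes bleeding precautions. A count lifted by a recent transfusion can meet the limit without showing the patient's own level. A transfusion-free interval protects the limit only if it ends at the sample, and exclusion 38 ends its interval at consent. Footnote a shows that the authors saw the problem for hemoglobin and dealt with it there, but not for platelets.

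The erythropoietin conflict works in the other direction. It admits nobody unsafe. It shuts out patients whom footnote a sets out to allow, or leaves a site that follows the footnote with an eligibility deviation.

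**Working it through.** No sample size, power or alpha figure depends on this point. The check is day arithmetic on the windows, then a comparison of the texts.

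**Step 1. How much of the week before the sample does exclusion 38 cover?**
Let g be the days from consent to the qualifying sample, negative if a routine count taken before consent is used. Exclusion 38 covers the 7 days ending at consent, which are days g to g + 7 before the sample. The yardstick is the criterion's own 7-day length, placed so that it ends at the sample. The overlap is max(0, 7 − |g|).

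| g (days) | Days covered, of 7 |
|---|---|
| −3 | 7 − 3 = 4 |
| 0 | 7 |
| 3 | 7 − 3 = 4 |
| 6 | 7 − 6 = 1 |
| 7 or more | 0 |

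**Step 2. When is g at least 7?**
Let s be the days from consent to first dose (at most 28) and t the days from sample to first dose (0 to 7). Then g = s − t. With consent on day −28, g runs from 28 − 7 = 21 to 28 − 0 = 28, and coverage is 0. For any s of 14 or more, g is at least 14 − 7 = 7, so coverage is 0 whichever day the sample is taken. A re-test needs no new consent, so the anchor stays put while the sample moves later.

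**Step 3. Does another rule close the gap?**

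| Provision | Effect on a post-consent platelet transfusion |
|---|---|
| Table 5-1, footnote a | None: packed red cells only |
| Exclusion 13 (any bleeding diathesis) and exclusion 14 (Grade 3 or higher bleeding within 28 days before treatment) | Remove many patients transfused for bleeding; do not reach prophylactic transfusion |
| Eligibility re-check before first dose (Table 1-1) | Reapplies exclusions 13, 14 and 43; exclusion 38 re-read still looks back from consent |
| Sponsor approval of a re-test (Section 5.4) | Discretionary, with no transfusion condition; not triggered if the first qualifying sample follows the transfusion |
| Exclusion 43 | Rests on the investigator's opinion |
| Sections 6.5 and 6.5.3 | Arguable; neither names blood products |

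None expressly bars a platelet transfusion given after consent for a reason other than bleeding.

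**Step 4. Erythropoietin.**
Take 3 months as about 91 days, counted to first dose (footnote a gives no reference date). Consent is 0 to 28 days before first dose. Time on a stable dose at consent is then 91 − 28 = 63 to 91 − 0 = 91 days. The look-back is 28 days, and 63 exceeds 28, so the whole look-back lies inside the stable-dose period. Counting the 3 months to consent only lengthens the overlap. Provided a dose is given at least every 4 weeks, exclusion 38 applies every time, and because one exclusion is enough, the allowance never operates.

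**The case against.** The best defence is Section 6.5.3. It prohibits therapies during screening as well as treatment, points to the exclusion criteria for further prohibited medications, and says that participants who need the prohibited treatments should leave the study. Section 6.5 makes a similar statement. If blood products count as medications, exclusion 38 carries through screening and the gap closes. That reading is open, but neither section mentions transfusion, and Section 6.5.4 permits supportive care. An entry rule should not depend on it.

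The other checks in the Step 3 table also have force: together they would stop many cases. Later harm is limited too. Platelets are in Panel B from W2. Table 6-3 has regorafenib held and reduced for Grade 3/4 thrombocytopenia, and pembrolizumab held at Grade 3 or discontinued at Grade 4. The SAP's version history records that recruitment stopped early, so new wording would protect no further participant in this trial.

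A reader might go further in two ways that the documents do not support.
- One is to call exclusion 38 the only consent-anchored window in Section 5.2. Exclusion 26 also counts from consent, although it sits under another sub-heading and states an allowance. The contrast holds only within the prior and concomitant therapy group.
- The other is to hold platelets to footnote a's 2-week interval. That is a red-cell rule; no document sets such an interval for platelets.

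On erythropoietin, it is fair to reply that the conflict resolves on the cautious side. It remains a contradiction between two eligibility texts.

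**Conclusion.** Both parts hold, and the point is minor.

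On platelets, once the qualifying sample is 7 or more days after consent, exclusion 38 covers 0 of the 7 days before it. No eligibility rule expressly prevents a non-bleeding platelet transfusion from meeting the 60 000/mm³ limit. This assumes that the criterion's own 7 days is the length intended, and that Sections 6.5 and 6.5.3 are not read to include blood products. It counts days without an express rule; it is not an estimate of how often such a transfusion happens, which the documents do not give. A reader might infer that under-qualified patients were in fact enrolled, or that the response rate is affected. Nothing in the documents supports either inference.

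On erythropoietin, the allowance in footnote a has no effect, assuming a dose at least every 4 weeks.

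**What to change.** 1. In exclusion 38, count the transfusion window back from the qualifying laboratory sample, including any re-test. Alternatively, extend footnote a of Table 5-1 to platelet transfusion for the platelet limit.
2. Either exempt stable-dose erythropoietin from exclusion 38, or delete the allowance from footnote a.

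The cost is the wording of one criterion and one footnote, and possibly a few more screen failures. Sample size, alpha, power and the ORR analysis do not change. With recruitment closed, the practical use is in any later protocol that reuses this eligibility text.
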